Study Design:	
This study is a single-site, prospective, observational clinical study of Cytal® Wound Matrix alone or in combination with MicroMatrix® for the management of wounds.
 
In this study, Cytal® Wound Matrix 1-Layer will be applied topically to study wounds, with MicroMatrix® applied to fill the base of deep wounds (exceeding 3mm in depth) according to product use instructions. Patients with diverse wound types will be observed in the study, including patients with venous ulcers, diabetic foot ulcers, pressure ulcers, trauma wounds, external surgical wounds, and wound dehiscence/surgical site infection.
 
Patients may undergo weekly treatment for their wounds and can be treated with up to 10 applications of Cytal® (with MicroMatrix® when wound depth exceeds 3mm) within the first 12 weeks, including unscheduled visits (within this 12 week period). If the Subject has multiple wounds, the most-appropriate wound that meets inclusion criteria and has at least two cm of healthy tissue between itself and other wounds (as determined by the investigator) will be selected as the Study Wound. A protocolized standard of care will be followed for Study Wounds in addition to the application of Cytal® and MicroMatrix® (i.e. surgical debridement, offloading etc. as appropriate for the particular wound type and severity).

Objectives:	
Primary Objective
 
The primary objective is to assess the effect of Cytal® with or without MicroMatrix® on primary measures of wound healing efficacy.
 
Secondary Objective(s)
 
 1. Assess the effect of Cytal® with or without MicroMatrix® on secondary measures of wound healing efficacy. 2. Assess effect of treatment on patient-reported quality of life at baseline and at time of healing or at 12 weeks if the wound remains unhealed. 3. Assess complete wound management. 4. Wound-related adverse events. 
Tertiary Objective(s)
 
 1. Assess costs of treatment and patient work status.

	
2. Assess wound pathology.


Endpoints:
	
Primary Endpoint
 
1. Effect of Cytal® with or without MicroMatrix® on primary measures of wound healing efficacy will be assessed by determining:
 
 a. Number and percentage of wounds with area reduced by greater than or equal to 40% by week 4, 60% by week 8, and 80% by week 12 as determined by wound image planimetry for each wound type. b. Number and percentage of completely healed wounds (100% epithelialization) by 12 weeks for each wound type. This will be verified by investigators and through a blinded review of wound photos by independent wound physicians. 
Secondary Endpoints
 
1. Secondary measures of wound healing efficacy will be assessed through week 12 by determining:
 
 a. Time to complete wound closure as determined by wound image planimetry using the Silhouette Star camera system by Aranz®. b. Wound characteristics including granulation tissue quality and presence/quantity of exudate as determined by standardized clinician evaluation. c. Incidence of bridging to definitive closure such as graft, flap (when bridging is the goal of treatment), or transition to cellular therapy as determined by investigator. 
2. Effect of treatment on patient-reported quality of life will be assessed by Visual Analog Scale (VAS), Wound Quality of Life (W-QOL), and Katz ADL health-related quality of life surveys at healing or at 12 weeks if the wound remains unhealed.
 
3. Complete wound management will be assessed through week 12 by recording the following on a standardized questionnaire:
 
 a. Method of application of Cytal®/MicroMatrix® and how the product is secured (e.g. sutures, steri-strips). b. Adjunctive treatments and dressings (e.g.

	
debridement, offloading, negative pressure wound therapy, hyperbaric oxygen).
 
4. Number and type of wound-related adverse events through week 12 as recorded on adverse event case report forms.
 
Tertiary Endpoints
 
1. Costs of treatment and patient work status through week 12 will be assessed by the following:
 
 a. Direct wound-related costs will be calculated and stratified by product and care cost. b. Current employment status and return to work status will be recorded and frequency of changes will be assessed. c. Measure frequency of wound specific AEs, and SAEs. 
2. Wound Pathology will be assessed through week 12 by the following:
 
 a. Effect of treatment with Cytal® with or without MicroMatrix® on pro-inflammatory and anti-inflammatory macrophage biomarkers, vascularization, and fibrosis in wound tissue biopsies will be assessed through quantitative image analysis for the following stains: 
 i. CD86 and CD163 immunostains to quantify pro-inflammatory M1 and anti-inflammatory M2 macrophage phenotypes. ii. CD31 immunostain to quantify vascularization. iii. Masson’s trichrome to quantify fibrosis. b. Pathologists’ findings over the course of treatment will be assessed by quantification of standardized pathologists’ findings in wound pathology reports based on Hematoxylin and Eosin staining.

Number of Subjects:
	
Estimated 80 subjects for treatment. (Maximum of 100). Subjects who are screened and meet all eligibility are enrolled in the study.

Study Criteria:
	
Inclusion Criteria: (All inclusion criteria must be met for enrollment)
 
 1. Subject has at least one wound that the treating physician determines may be treated with Cytal® with or without MicroMatrix®. 2. Subject is ≥ 22 years of age.

	
 3. Subject is willing and able to adhere to protocol requirements and agrees to participate in the study program and comply with the study follow-up regimen. 4. Subject or legal representative is willing to provide informed consent. 5. For females of reproductive potential, confirmed negative pregnancy test at enrollment. 
Exclusion Criteria: (No exclusion criteria may meet for enrollment)
 
 1. Allergy or hypersensitivity to materials in porcine-based study products (per subject report) or personal preference. 2. Subject report of concurrent participation in another clinical trial that involves an investigational drug or device that would interfere with this study. 3. The subject has any physical or psychiatric condition that, in the Investigator's opinion, would warrant exclusion from the study or prevent the subject from completing the study. 4. The subject's wound shows evidence of infection as determined by the Principal Investigator (which may be indicated by presence of: elevated WBC, pus, moderate or greater discharge, abnormal odor, or acute osteomyelitis). 5. Wound with exposed organs or hardware. 6. Wound with burn etiology.
Number of Sites enrolling participants:	1 (NYU Winthrop Hospital)
ACell Study Products:	
 1. Cytal®™ Wound Matrix 1-Layer 2. MicroMatrix®
Participant & Study Duration:	
80 subjects are expected to complete this trial (maximum of 100 may be enrolled). The duration of participation for each subject will be up to a maximum of 55 weeks (1 week screening/treatment; 12 week follow-up; 26 week confirmation of wound closure/recurrence; 52 week final study visit). All visits have protocol stipulated windows.
 
Recruitment and enrollment efforts are expected to last for approximately 12 months, starting in June 2018. The study will end in approximately May 2019, with Last Subject Last Visit expected in May 2020.
 
The actual overall study duration or subject recruitment period may vary.

Statistical Methodology:	The objective of this study is to define the trajectory of healing using either 1 or 2 test products; the intra-patient change will be the focus

	
of the analyses, not the comparison of response between 1 vs. 2 product application.
 
All statistical tests to examine the change from baseline (study pre-treatment) will be conducted using a type 1 error rate of 5%. Simultaneous testing for the 2 primary endpoints will be conducted based on individual a priori thresholds. The analyses of the secondary endpoints will be conducted without adjustment for multiple testing.
 
The analysis of the primary endpoints will be based on a generalized linear model specifying the distribution as binomial. If a patient withdraws prior to completing the study, however the last recorded observation revealed the wound had closed, the patient will be counted in the primary analysis as having achieved complete wound epithelization. If a patient withdraws prior to the 12-week wound evaluation visit and the last recorded observation revealed the wound had not closed, the patient will be counted in the primary analysis as not having achieved complete wound epithelization. This procedure will be also be followed for the examination at the patients by the various percent reduction thresholds. The analyses of all non-primary endpoints will be based on the distribution of data. For continuous variables, descriptive statistics will be used and the change from baseline will be tested against a difference of zero. For binomial and multinomial variables, results will be presented using counts, percentages, and shift tables. The analysis of the time of the initial observation of complete wound epithelization will be reported using Kaplan-Meier estimates.

--	--

2. INTRODUCTION: BACKGROUND INFORMATION AND SCIENTIFIC RATIONALE

2.1 BACKGROUND INFORMATION AND RATIONALE

Treatment for acute and chronic wounds is evolving, and will likely continue to change as new therapies for the condition are developed and incorporated into standard of care. Micromatrix® and Cytal® received FDA 510(k) clearance (K152721 and K060888) based on required biocompatibility and performance data to manage chronic and acute wounds, including partial- and full-thickness wounds, pressure ulcers, venous ulcers, diabetic ulcers, chronic vascular ulcers, tunneled/undermined wounds, surgical wounds, trauma wounds, and draining wounds. This study is a prospective observational study to illustrate how Micromatrix® and Cytal® perform when used as a treatment system for multiple chronic wound types in clinical settings.

2.2 POTENTIAL RISKS AND BENEFITS

2.2.1 RISKS

Risks involved with this treatment are similar to risks of other standard treatments of wounds of this nature. Possible complications include infection, chronic inflammation (inflammation other than that which may occur immediately following application of product), allergic reaction, excessive redness, pain, swelling, or blistering. If any of these conditions occur, the dressing should be removed.

2.2.2 BENEFITS

This treatment may result in significant and/or complete healing of patients' wounds. If there is no improvement in healing, it is expected that the information gained in this study will be beneficial to wound care patients in the future.

3. OBJECTIVES AND PURPOSE

3.1 PRIMARY OBJECTIVES

The primary objective is to assess the effect of Cytal® with or without MicroMatrix® on primary measures of wound healing efficacy.

3.2 SECONDARY OBJECTIVES

1. Assess the effect of Cytal® with or without MicroMatrix® on secondary measures of wound healing efficacy.

2. Assess effect of treatment on patient-reported quality of life at baseline and at time of healing or at 12 weeks if the wound remains unhealed.
3. Assess complete wound management.
4. Wound-related adverse events.

3.3 TERTIARY OBJECTIVES

1. Assess costs of treatment and patient work status.
2. Assess wound pathology.

4. STUDY DESIGN AND ENDPOINTS

4.1 DESCRIPTION OF THE STUDY DESIGN

This study is a single-site, prospective, observational study of Cytal® Wound Matrix alone or in combination with MicroMatrix® for management of wounds. Cytal® and MicroMatrix® both consist of decellularized porcine urinary bladder matrix (UBM). The processed UBM retains native extracellular matrix structure with intact epithelial basement membrane and numerous collagens that may promote improved wound healing. Cytal® consists of single- or multilayer sheets of UBM, while MicroMatrix® is a micronized powder form of UBM. Both products are FDA 510k cleared (K152721 and K060888) for use in the management of wounds.

In this study, Cytal® Wound Matrix 1-Layer will be applied to study wounds, with MicroMatrix® applied topically to fill the base of deep wounds (exceeding 3mm in depth) according to product use instructions. Patients with diverse wound types will be observed in the study, including but not limited to patients with venous ulcers, diabetic foot ulcers, pressure ulcers, trauma wounds, external surgical wounds, and wound dehiscence/surgical site infection.

Patients may undergo weekly treatment for their wounds and can be treated with up to 10 applications of Cytal® (with MicroMatrix® when wound depth exceeds 3mm) within the first 12 weeks. If the Subject has multiple wounds, the most-appropriate wound that meets inclusion criteria and has at least two cm of healthy tissue between itself and other wounds (as determined by the investigator) will be selected as the Study Wound. A protocolized standard of care will be followed for Study Wounds in addition to the application of Cytal® and MicroMatrix® (i.e. surgical debridement, offloading etc. as appropriate for the particular wound type and severity).

4.1.1 PRIMARY ENDPOINT

1. Effect of Cytal® with or without MicroMatrix® on primary measures of wound healing efficacy will be assessed by determining:

- a. Number and percentage of wounds with area reduced by greater than or equal to 40% by week 4, 60% by week 8, and 80% by week 12 as determined by wound image planimetry for each wound type.
- b. Number and percentage of completely healed wounds (100% epithelialization) by 12 weeks for each wound type. This will be verified by investigators and through a blinded review of wound photos by independent wound physicians.

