10. STATISTICAL CONSIDERATIONS

10.1 DESCRIPTION OF STATISTICAL METHODS

Wound area will be analyzed for size, percentage closure on weekly basis. The mean, median and standard deviations will be calculated and scatter plots developed to determine healing rates by application number, and days in treatment. The mean number of application of product will be tabulated.

All statistical tests to examine the change from baseline (study pre-treatment) will be conducted using a type 1 error rate of 5%. Simultaneous testing for the 2 primary endpoints will be conducted based on individual a priori thresholds. The analyses of the secondary endpoints will be conducted without adjustment for multiple testing.

The analysis of the primary endpoints will be based on a generalized linear model specifying the distribution as binomial. If a patient withdraws prior to completing the study, however the last recorded observation revealed the wound had closed, the patient will be counted in the primary analysis as having achieved complete wound epithelization. If a patient withdraws prior to the 12-week wound evaluation visit and the last recorded observation revealed the wound had not closed, the patient will be counted in the primary analysis as not having achieved complete wound epithelization. This procedure will also be followed for the examination of the patients by the various percent reduction thresholds. The analyses of all non-primary endpoints will be based on the distribution of data. For continuous variables, descriptive statistics will be used and the change from baseline will be tested against a difference of zero. For binomial and multinomial variables, results will be presented using counts, percentages, and shift tables. The analysis of the time of the initial observation of complete wound epithelization will be reported using Kaplan-Meier estimates. The sample size for this clinical investigation was derived based on establishing sufficient precision among the different endpoints to be able to reliably estimate the expected effect of the 2 product used either alone or in combination. For proportions, the length of the 2-sided 95% confidence interval from the proportion to the limit with 80 patients is between 9% and 10% (ref. table presented below).

Scenario	Lower 95% Exact Confidence Limit (%)	Percentage of Patients Who Respond	Upper 95% Exact Confidence Limit (%)
1	15.99	25.00	35.94
2	26.92	37.50	49.04
3	30.33	40.00	50.28
4	50.96	62.50	73.08

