5	64.06	75.00	84.01

For mean changes from baseline, if the standard deviation of the difference from baseline for a parameter is 10 units, the confidence level will exceed 90% with a distance from the mean to the limit as small as 2 units.

For data derived from a binomial distribution and a continuous distribution, 80 patients should be sufficient to detect a clinically-meaningful change in this clinical investigation.

In summary, the sample size for this clinical investigation is sufficient to detect a 34% difference in the proportion of responders between the 2 treatments (power: 81.9%, alpha: 5%, 40 patients per treatment arm with 30% response and 64% response, respectively). If the observed proportion of response between the 2 treatment arms is 15% and 46% respectively, with 40 patients per treatment arm, the power will be 81.1%. If there is an imbalance between the 2 treatment arms (30 patients and 50 patients, respectively), and observed proportion of response between the 2 treatment arms is 15% and 47%, the power will be 80.3%.

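### The stated 9 to 10 point precision is for 80 pooled patients, not for the wound-type rates that define the primary endpoints, and is too narrow even for the pooled rate

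*Combined protocol and SAP*

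**What the plan says.** Section 4.1.1 and the Protocol Summary give two primary endpoints. The first counts wounds that reach set area reductions at weeks 4, 8 and 12, ending with "80% by week 12 as determined by wound image planimetry for each wound type". The second is the "Number and percentage of completely healed wounds (100% epithelialization) by 12 weeks for each wound type". Section 4.1 names six wound types and leaves the list open: "Patients with diverse wound types will be observed in the study, including but not limited to patients with venous ulcers" and others.

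Section 10.1 says of the analysis: "The analysis of the primary endpoints will be based on a generalized linear model specifying the distribution as binomial". It names no wound-type term, stratum or pooling rule, and sets no minimum number per type. It plans simultaneous testing of the two primary endpoints against prespecified thresholds, but does not say whether the tested rate is pooled or by type. On precision it says that the length of the two-sided 95% interval "from the proportion to the limit with 80 patients is between 9% and 10" percent, and adds a table of exact limits for five response rates.

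Section 10.2 puts the cohort at an estimated 80 treated subjects (maximum 100), covering all wounds managed with the products. Section 5.3 instead describes 80 as the number expected to complete after about 20% dropout, with at most 100 enrolled.

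**The concern.** Section 10.1 gives precision of estimation as the basis for the sample size, so the precision figure is what tells a reader what the study can deliver. As the endpoints are written, the primary results are a set of rates, one per wound type, each resting on only part of the cohort. The quoted figure belongs to a different quantity, the rate over all 80 patients. Nothing in Section 10 links the two. The plan therefore gives no precision for its primary endpoints as defined, and leaves open which rate the planned tests concern. The quoted figure also disagrees with the table printed beneath it.

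**Working it through.** **Inputs.** From Section 10.1: n = 80, two-sided 95% exact limits, and the five tabulated rates. From Section 4.1: six named types. From Sections 5.3 and 10.2: 80 and a maximum of 100 subjects. Patients per type are not given, so the values used below are assumptions.

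**Method.** For x responders out of n, the exact (Clopper-Pearson) limits are L = Beta quantile(0.025; x, n−x+1) and U = Beta quantile(0.975; x+1, n−x). The plan's measure is the distance from the proportion to a limit, p − L or U − p, and that measure is used throughout.

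**Step 1: reproduce the table at n = 80.**

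| Rate | x/80 | Recomputed limits | Printed limits | Distances at n=80 |
|---|---|---|---|---|
| 25% | 20 | 15.99–35.94 | 15.99–35.94 | 9.01, 10.94 |
| 37.5% | 30 | 26.92–49.04 | 26.92–49.04 | 10.58, 11.54 |
| 40% | 32 | 29.20–51.56 | 30.33–50.28 | 10.80, 11.56 |
| 62.5% | 50 | 50.96–73.08 | 50.96–73.08 | 11.54, 10.58 |
| 75% | 60 | 64.06–84.01 | 64.06–84.01 | 10.94, 9.01 |

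Four rows match exactly, so the table is for all 80 patients together. The 40% row does not match; 40/100 gives 30.33–50.28, which is the printed row.

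**Step 2: check the 9 to 10 point statement.** The distances at n = 80 run from 9.0 to 11.6. The printed limits alone contradict the sentence: 62.50 − 50.96 = 11.54 and 35.94 − 25.00 = 10.94. Even the misplaced 40% row has 50.28 − 40.00 = 10.28, so every printed row has a limit more than 10 points away. The normal approximation does not rescue it: 1.96 × √(0.25 × 0.75/80) = 9.5 points at 25%, but 1.96 × √(0.40 × 0.60/80) = 10.7 points at 40%.

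**Step 3: which n?** Section 10.1 counts a patient who withdraws before week 12 with an unclosed wound as not healed, so that patient stays in the denominator. The analysed n could then approach 100. At n = 100 the distances for rates of 25% to 75% are 8.1 to 10.3 points.

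**Step 4: type-level rates, with assumed n.** An equal split over six types would give 80/6 ≈ 13 or 100/6 ≈ 17 patients per type. The other values bracket these.

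| Patients in the type | Exact 95% interval near 25% | Distance to a limit, rates of about 25–75% |
|---|---|---|
| 40 | 10/40: 12.7–41.2 | 12.3 to 16.7 |
| 25 | 6/25: 9.4–45.1 | 14.6 to 21.5 |
| 17 | 4/17: 6.8–49.9 | 16.7 to 26.5 |
| 13 | 3/13: 5.0–53.8 | 18.0 to 30.7 |
| 8 | 2/8: 3.2–65.1 | 21.8 to 40.1 |

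Even a type holding half of the 80 patients has both limits more than 12 points from the estimate.

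**The case against.** The strongest reply is that the wording by wound type only instructs how to tabulate, and that the pooled rate is what the study is about. There is support for this. The primary objective in Section 3.1 speaks of the effect "on primary measures of wound healing efficacy" without mentioning type, the binomial model has no type term, and Section 10.2 describes one cohort of all wounds. The precision sentence names 80 patients, so a careful reader is unlikely to apply it to a subgroup. The study is also single-site, uncontrolled and observational, which limits the harm. All of that stands, and it bears on how serious the point is. It does not remove the mismatch: no section names a pooled rate as an endpoint, and the endpoint definition is by type in both places where it appears.

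A reader might go further and infer that the plan names no primary rate, so that either result could be presented as primary after the data are seen. The documents do not support that. Read literally, the endpoint text does name the type-level rates; what is missing is any treatment of them in Section 10.

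A reader might also bring in the power statement in Section 10.1 ("sufficient to detect a 34% difference in the proportion of responders between the 2 treatments"), given that the Protocol Summary says the focus is "not the comparison of response between 1 vs. 2 product application". That conflict does not depend on wound type. It is a separate issue and adds no weight here.

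**Conclusion.** The point holds in two parts.

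- **Mismatch.** The stated precision applies to 80 pooled patients and does not describe the primary endpoints as defined. How much wider the type-level distances are depends on a split that the documents do not give: about 12 to 17 points at 40 patients in a type, up to 22 to 40 at 8. These are illustrations over assumed sizes and do not predict the mix that will be recruited.
- **Arithmetic.** For the pooled rate at n = 80 the correct range is 9.0 to 11.6 points, not 9 to 10, and one table row belongs to n = 100. This part needs no assumption about wound mix.

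The findings do not show that 80 patients are too few, because the plan sets no type-level precision target. The matter should be corrected, but the data to be collected remain usable.

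**What to change.** **In Section 10.1:**

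- Restate the precision as about 9 to 12 points at n = 80, for the all-wounds rate only.
- Correct the 40% row to 29.20–51.56.
- Say whether n means completers or all treated patients. If it can reach 100, give the corresponding distances of about 8 to 10 points.
- Add distances to the limit for type-level rates over a range of n, such as 40, 25, 17, 13 and 8.

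**In Section 4.1.1 and the Protocol Summary,** align the endpoints with Section 10 in one of two ways:

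- (a) Make the all-wounds rate primary, with an exact 95% interval, and report type-level rates descriptively with exact intervals.
- (b) Keep the type-level rates primary and drop the 9 to 10 point claim for them.

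Under either option, state to which rate the planned testing against prespecified thresholds applies, in Section 10.1 and in the Protocol Summary.

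**Cost.** This is an amendment of wording, with IRB review under Section 13.2, and adds no patients, visits or data. The stated precision becomes less favourable. Under (a) the pooled rate depends on the mix of wound types recruited; under (b) the primary estimates are openly imprecise for small types.
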